## Statistical Analysis Plan

Sponsor Name: Nitto Denko Corporation  
Sponsor Protocol ID: ND-L02-s0201-005

- treatment-emergent AEOI by SOC and PT;
- serious treatment-emergent AEOI by SOC and PT;
- treatment-emergent AEOI leading to study treatment interruption by SOC and PT;
- treatment-emergent AEOI leading to study treatment withdrawn by SOC and PT.

- [REDACTED]
- [REDACTED]

No statistical comparisons of AEs between treatment arms will be performed.

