## **6. STUDY OBJECTIVES**

### **6.1. Primary Objective**

- Evaluate the safety and tolerability of ND-L02-s0201, administered at 2 dose levels, Q2W over 24 weeks, versus placebo, in conjunction with standard of care (SOC)

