## 13. STATISTICS

In addition to this section of the study protocol, a Statistical Analysis Plan (SAP) will be developed and finalized prior to the final database lock and unblinded data analysis. The SAP will provide a detailed description for the handling of missing data, subject eligibility criteria for the analysis, and statistical methodology for the data summary and between-group comparisons.

Statistical analysis will be done by the Sponsor or under the authority of the Sponsor. A general description of the statistical methods to be used to analyze the safety and efficacy data is outlined below. Specific details will be provided in the SAP.

Additional sensitivity analyses may be performed due to the COVID-19 pandemic. All analyses related to COVID-19 will be conducted in accordance with regulatory guidelines. These analyses will be described in the SAP.

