### **13.2.3. Safety**

All safety analyses will be performed on the safety population.

The analysis of safety, reported for each treatment arm, will be based on the frequency of AEs and their severity for all treated subjects. The safety variables, including AEs, SAEs, and AEs of interest (coded using the Medical Dictionary for Regulatory Activities [MedDRA]), clinical laboratory tests [REDACTED] physical examination, ECGs, and vital signs will be summarized or tabulated by treatment arm. Some of the variables will be tabulated by treatment arm and by visit. Incidence of AEs will be further tabulated by subjects on SOC within each treatment arm.

The proportion of subjects discontinuing study treatment due to AEs will be tabulated by treatment arm.

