### 2. Protocol Details

#### 2.1 Study Objectives

Primary:

- Evaluate the safety and tolerability of ND-L02-s0201, administered at 2 dose levels, once every 2 weeks (Q2W) over 24 weeks, versus placebo, in conjunction with standard of care

Secondary:

- Evaluate the biological activity of ND-L02-s0201 as measured by spirometry over 24 weeks
- Evaluate changes of interstitial lung abnormalities (ILA) as measured by high-resolution computed tomography (HRCT)

- [REDACTED]
- [REDACTED]

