## 3. Efficacy and Safety Variables

### 3.1 Primary Endpoints

#### Safety

- Incidence of TEAEs and treatment-emergent SAEs
- Proportion of subjects discontinuing study treatment due to TEAEs

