## Statistical Analysis Plan

Sponsor Name: Nitto Denko Corporation  
Sponsor Protocol ID: ND-L02-s0201-005

the corresponding times have not been recorded. Measurements that are obtained after the first date of study treatment will be considered post-baseline values. Change from baseline is defined as (post-baseline value – baseline value).

Time-to-event endpoints will be summarized using Kaplan-Meier (KM) method to estimate the median, and the 25th and 75th percentiles.

The following principles will be applied to all TFLs unless otherwise stated:

Principle	Value
Treatment arm labels and order presented	1. Placebo 2. ND-L02-s0201 45 mg 3. ND-L02-s0201 90 mg 4. Total (if applicable)
Tables	Data in summary tables for safety will be presented by treatment arm, and Total, and visit (where applicable). Data in summary tables for efficacy will be presented by treatment arm.
Listings	All data collected presented by treatment arm, subject, and visit date (where applicable), unless otherwise specified.
Descriptive summary statistics for continuous variables	Number of subjects (n), mean, standard deviation, median, minimum, maximum
Descriptive summary statistics for categorical variables	Frequency counts and percentages [n (%)]
Denominator for percentages	By-visit summaries: number of subjects with non-missing data at the visit assessed in the analysis population of each treatment arm; Other summaries: Number of subjects in the analysis population of each treatment arm, unless specified otherwise.
Include "Missing" as category	Included for demographics and other baseline characteristics when the number of missing is greater than zero for at least one treatment arm. Missing post-baseline values will not be summarized, unless otherwise specified.
Display for percentage	One decimal place, except for 100%
Display for 0 percentages	blank
Display to one more decimal place than collected value	Mean, Median

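### The primary objective is safety versus placebo, but the primary AE endpoints get only counts and percentages by arm, with no estimated difference from placebo and no interval

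*SAP*

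**What the plan says.** The objective is worded as a comparison. Protocol 6.1 reads "Evaluate the safety and tolerability of ND-L02-s0201, administered at 2 dose levels, Q2W over 24 weeks, versus placebo", and SAP 2.1 has the equivalent wording. Allocation is 1:1:1 with a concurrent placebo arm.

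The primary endpoints (Protocol 13.1.1, SAP 3.1) are "Incidence of TEAEs and treatment-emergent SAEs" and "Proportion of subjects discontinuing study treatment due to TEAEs", which makes three proportions.

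SAP 7.6.2 summarises these by arm and overall in the safety population. The general rules in SAP 7.1 give n and percent as the summary for categorical variables. The section closes with "No statistical comparisons of AEs between treatment arms will be performed".

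The protocol's own safety analysis (13.2.3) is also tabular: "The proportion of subjects discontinuing study treatment due to AEs will be tabulated by treatment arm". The introduction to Protocol section 13 says more generally that the SAP will describe "statistical methodology for the data summary and between-group comparisons".

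SAP 7.5.2.4 and 7.5.2.5 treat several clinical events differently. Acute IPF exacerbation, respiratory hospitalization, all-cause mortality, and transplantation or death get chi-squared tests, exact 95% CIs including differences from placebo, stratified log-rank tests and hazard ratios.

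**The concern.** A randomized, placebo-controlled trial with a comparative primary objective should say how far each dose differs from placebo on its primary endpoints, and with what uncertainty. Here the reader gets three columns of percentages and compares them by eye. With about 40 subjects per column, a small observed gap can be taken as reassurance when a large excess is not excluded. A gap that is within chance can equally be taken as a signal.

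The plan also gives more estimation to secondary clinical events than to its primary endpoints. One of those events, acute IPF exacerbation, is identified from the AE form (SAP 7.5.2.4) and listed as an AE of special interest (SAP 3.4.6). An unqualified bar on comparing AEs and a section that compares this AE cannot both be followed to the letter.

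**Working it through.** **1. The plan's own figure.** Protocol 13.3 and SAP 2.3 give about 120 subjects, about 40 in each of 3 arms: 3 × 40 = 120, which agrees. The stated 35-40 sites with 3-5 subjects each give 35 × 3 = 105 to 40 × 5 = 200, a range that contains 120. The visible text states no power, margin, AE rate or precision target, so nothing further can be reproduced.

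**2. Is an estimate planned anywhere?** The overview table in SAP 7.6.2 contains all three primary proportions as number and percent of subjects. The visible parts of SAP 3.1, 7.1, 7.6.2 and 8 contain no difference, ratio or interval for any of them.

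**3. What an interval would show.** The documents give no AE rates, so the rates below are assumptions, shown as a range. With n = 40 per arm and z = 1.96, the Wilson limits for one arm are

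[p + z²/2n ± z·√(p(1−p)/n + z²/4n²)] / (1 + z²/n).

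The Newcombe interval for p1 − p2 combines the Wilson limits (l, u) of the two arms:

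- lower = (p1 − p2) − √[(p1 − l1)² + (u2 − p2)²]
- upper = (p1 − p2) + √[(u1 − p1)² + (p2 − l2)²]

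Worked case, 2/40 in both arms (5%): z²/n = 0.0960. The Wilson limits are (0.05 + 0.0480 ± 1.96 × √(0.0011875 + 0.00060025)) / 1.0960, that is 0.0138 and 0.1650. The half-width is √(0.0362² + 0.1150²) = 0.121, or 12.1 points.

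| Assumed rate, both arms | Newcombe half-width (points) | Wald half-width, 1.96·√(2p(1−p)/40) |
|---|---|---|
| 5% | 12.1 | 9.6 |
| 10% | 14.4 | 13.1 |
| 20% | 17.6 | 17.5 |
| 30% | 19.5 | 20.1 |
| 50% | 20.9 | 21.9 |

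The Wald interval is too narrow at low incidence, where SAEs and discontinuations may lie. At 0/40 versus 0/40 its width is zero, whereas Newcombe gives 0.0960/1.0960 = 0.088, or about 8.8 points. The method therefore has to be one that is valid at low counts.

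**4. Unequal observed rates (Newcombe).**

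- 8/40 versus 4/40: +10 points (95% CI −6.1 to 25.9).
- 12/40 versus 4/40: +20 points (2.3 to 36.6).

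**5. Why intervals and not tests.** Power at 40 per arm and two-sided 0.05 is Φ{[|p1 − p2| − 1.96·√(2p̄(1−p̄)/40)] / √[(p1(1−p1) + p2(1−p2))/40]}, where p̄ is the mean of the two rates.

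- 10% versus 20%: (0.10 − 0.1565)/0.0791 = −0.71, so power is 24%.
- 10% versus 30%: (0.20 − 0.1753)/0.0866 = 0.285, so power is 61%.

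A p-value would say little at this size. An interval says what is and is not excluded.

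**The case against.** **The SAP follows the protocol.** Protocol 13.2.3 plans tabulation by arm, and the SAP delivers it. The reference to between-group methods in Protocol section 13 is general and does not promise them for AEs. Descriptive AE reporting is common in phase 2, and no safety hypothesis or margin is stated. All of this stands, and it is why the point is not an error.

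**Comparison is not forbidden altogether.** A reader might infer that 7.6.2 rules out comparing the arms in any form. It does not: it bars statistical comparisons, and the side-by-side display by arm is itself a descriptive comparison with placebo.

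**Some grave harms already have contrasts.** A reader might also infer that no harm is estimated against placebo. SAP 7.5.2.4 and 7.5.2.5 cover mortality, respiratory hospitalization, exacerbation, and transplantation or death. They do not cover overall TEAE incidence, SAE incidence or discontinuation due to TEAEs. Those sections are also not a template to copy, because they define rates per 100 patient-years and then apply chi-squared tests and intervals for proportions.

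**The consequence is limited.** Counts and denominators will be reported by arm, so a reader can compute the interval later. The DMC reviews safety separately (Protocol 7.4), so no stopping decision depends on this table. Both statements are true, but neither is a reason to leave the primary comparison to the reader.

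**Redaction.** Bullets directly before the sentence in 7.6.2 are blacked out. The sentence is unqualified, so they are unlikely to hold a primary-endpoint comparison, but this cannot be ruled out.

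**Conclusion.** The point holds as a gap in reporting. In the visible text, the three primary proportions have no estimated difference from placebo and no interval, although the objective is comparative. With 40 per arm and equal observed rates, differences of about 12 points (at 5%) to about 21 points (at 50%) would not be excluded. These figures rest on assumed rates, on 40 evaluable subjects in each arm and on Newcombe intervals.

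There is a smaller drafting conflict as well: the unqualified sentence in 7.6.2 and the formal comparison of exacerbation in 7.5.2.4 need to be reconciled.

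The documents do not support calling this an error or a departure from the protocol, and nothing the plan computes becomes wrong. It is a cheap improvement.

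**What to change.** Replace the closing sentence of SAP 7.6.2 with:

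> For each dose versus placebo, the risk difference with a 95% CI (by a method valid at low counts, such as Newcombe or exact) will be given for the incidence of TEAEs, treatment-emergent SAEs and discontinuation of study treatment due to TEAEs in the safety population. Apart from the secondary endpoint analyses in 7.5.2.4 and 7.5.2.5, no hypothesis tests of AEs will be performed; SOC/PT tables remain descriptive.

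Name one interval method in the final text so that the choice is fixed before unblinding.

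**Cost.** One extra table with 3 endpoints × 2 doses = 6 risk differences. The intervals will be wide and unadjusted for multiplicity, and some readers may treat them as six tests, so a footnote should say that they are descriptive.

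**Limit.** A crude risk difference ignores unequal time at risk. The TEAE window closes two weeks after the last dose (Protocol 14.2.1, SAP 3.4.6), so early discontinuation shortens it. If discontinuation differs between arms, an exposure-adjusted rate difference beside the crude one would help.

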### 7.6.3 Laboratory Evaluations

All laboratory data will be reported in conventional units. Reference range will be presented in the listing. Out-of-reference-range values will be flagged as high (H) or low (L) in the listings.

Laboratory data will be summarized by treatment arm, overall, and visit using standard descriptive statistics for the SAF population. Changes from baseline will also be summarized.

For hematology and serum chemistry, shift tables presenting movement in and out of reference range from baseline to each scheduled post-baseline visit will be provided for each treatment arm.

[REDACTED]

- [REDACTED]
- [REDACTED]
- [REDACTED]

For subjects with abnormal baseline values, the following summary will also be created:

## Statistical Analysis Plan

Sponsor Name: Nitto Denko Corporation  
Sponsor Protocol ID: ND-L02-s0201-005

- ALT or AST >2x Baseline or total bilirubin >1.5x Baseline
- ALT or AST >2x Baseline and a concomitant total bilirubin >2x Baseline
- If baseline measurements were <2.5x ULN: ALT or AST >5x baseline

For all subjects, number of subjects with elevated ALT or AST and Total Bilirubin following the Hy's Law (ALT or AST >3X ULN and Total Bilirubin >2X ULN) will be summarized. The onset date of ALT or AST elevation should be prior to or on the date of Total Bilirubin elevation. Additionally, Evaluation of Drug Induced Serious Hepatotoxicity (eDISH) plots will be generated for peak total bilirubin vs peak ALT and peak AST.

Box-plots of the absolute value of lab tests at each scheduled visit will be provided. All lab tests results will also be listed.

### 7.6.4 Vital Signs and Pulse Oximetry

Vital signs and SpO2 data and changes from baseline in vital signs and SpO2 will be summarized by visit using standard descriptive statistics for the SAF population. For visits that have vital sign data collected before, during, and after study treatment infusion, the pre-infusion vital sign will be included in the summary table. A table for change from pre-infusion will also be provided for the visits with multiple vital sign measurements before, during, and after study treatment infusion. Vital sign findings per subject will be detailed in a listing.

### 7.6.5 Electrocardiograms

The ECG measurements and changes from baseline in ECG will be listed and summarized by treatment arm and visit using standard descriptive statistics for the SAF population. For visits (visit 4 and visit 8) where both pre-infusion and post-infusion ECG are measured, the pre-infusion ECG will be included in the summary table of change from baseline. In addition, difference of ECG measurements between pre-infusion and post-infusion of study treatment for visit 4 and visit 8 will be listed and summarized.

The number and percent of subjects with the averaged QT interval (msec) and Fridericia's corrected QT (QTcF) interval (msec) meeting below criteria will be summarized by treatment arm for baseline and post-baseline visits:

- QT interval >450 msec;
- QT interval >480 msec;
- QT interval >500 msec;
- QTcF interval >450 msec;
- QTcF interval >480 msec;
- QTcF interval >500 msec.

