### 3.4.10 12-Lead Electrocardiograms

The following quantitative ECG measurements will be taken during the study:

- heart rate (bpm);
- RR interval (msec);
- PR interval (msec);
- QRS interval (msec);
- QT interval (msec);
- Fridericia's corrected QT (QTcF) interval (msec).

An overall investigator assessment of ECG will be provided (categories "normal", "abnormal, not clinically significant" and "abnormal, clinically significant"). Clinically significant changes not already noted or significantly worsened than documented in Medical History will be recorded as AEs.

The baseline value will be defined as last scheduled or unscheduled value collected prior to start of study treatment. Assessments carried out on day of first study treatment administration are considered to have taken place before the drug administration, if the corresponding times have not been recorded. For post-baseline, only data from scheduled visits will be included in the summary tables. When triplicate ECG tracings are obtained at a study visit or timepoint, the triplicate average (or if fewer, average of ECGs available) will be included in the analysis.

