f Other abbreviated physical examinations may be performed at the discretion of the Investigator on the basis of signs or symptoms. See Section 11.1.3 for more information.

g During Visit 4 (Day 29), ECGs will be performed once, within 30 minutes after the end of the study treatment infusion.

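### The QT/QTcF outlier counts in SAP 7.6.5 mix pre-existing with newly arising values, so the table cannot show how many subjects crossed a limit on treatment

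*SAP*

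**What the plan says.** SAP 7.6.5 lists six criteria, three for QT and three for QTcF. The QTcF ones are "QTcF interval >450 msec", "QTcF interval >480 msec" and "QTcF interval >500 msec". Subjects "meeting below criteria will be summarized by treatment arm for baseline and post-baseline visits". All six are absolute limits. None is restricted to subjects who were at or below the limit before treatment, and none uses the size of a rise.

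The same section also plans a continuous summary: "The ECG measurements and changes from baseline in ECG will be listed and summarized by treatment arm and visit using standard descriptive statistics". The general principles in SAP 7.1 define those statistics: "Number of subjects (n), mean, standard deviation, median, minimum, maximum".

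A baseline for each subject already exists. SAP 3.4.10 states: "The baseline value will be defined as last scheduled or unscheduled value collected prior to start of study treatment".

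On timing, footnote g of SAP Appendix 2 repeats the protocol: "During Visit 4 (Day 29), ECGs will be performed once, within 30 minutes after the end of the study treatment infusion". Protocol Table 1 and section 12.3 also schedule an ECG at Visit 14/ET. SAP 7.6.5, by contrast, describes pre- and post-infusion ECGs at Visits 4 and 8.

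**The concern.** An outlier table should show how many subjects in each arm moved into a range of concern after dosing. Two unlinked counts, one at baseline and one post-baseline, do not show that. The post-baseline count contains subjects who were already high and stayed high, together with subjects who became high. With about 40 subjects per arm (SAP 2.3), one or two long-standing high values can make up a large part of the count.

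Subjects may be up to 80 years old, and no visible eligibility criterion limits QTcF. Inclusion 11 and exclusion 7 are redacted, so it is unknown how many subjects could enter above 450 msec.

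The SAP links each subject to his or her own baseline elsewhere. SAP 7.6.3 plans shift tables from baseline for hematology and chemistry, and multiples of baseline for liver tests in subjects with abnormal baseline values. Safety is the primary objective, so the ECG table could reasonably be built the same way.

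**Working it through.** The SAP states no QTcF count, sample size or power, so there is no figure to reproduce. The rule can be checked without assumptions. Its size can only be illustrated.

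**1. The rule applied to example subjects**

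| Baseline (msec) | Post-baseline (msec) | Change (msec) | Counted post-baseline >450? | New onset? |
|---|---|---|---|---|
| 455 | 455 | 0 | yes | no |
| 445 | 452 | +7 | yes | yes |
| 380 | 445 | +65 | no visible category | no |

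The first two subjects look the same in the post-baseline row. The third enters none of the visible categories.

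**2. What two separate counts can reveal**

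Let B of N subjects be above the limit at baseline and P post-baseline. The number who crossed upward can be anything from max(0, P − B) to min(P, N − B). With N = 40 and B = P = 4, that is 0 to 4: the same four subjects, or four new ones while the first four fell back. The table cannot separate these cases.

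**3. Stable high values**

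If an assumed 2.5%, 5%, 10% or 20% of an arm of 40 has a stable baseline above 450 msec, then 40 × that share = 1, 2, 4 or 8 subjects enter the post-baseline count with no drug effect.

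**4. Illustration with measurement variation and no drug effect**

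The inputs are assumptions, because the documents give none. Baseline and one post-baseline QTcF are bivariate normal with the same mean m, the same SD s and correlation r. Let z = (450 − m)/s.

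- Counted by the written rule, per 40: 40 × [1 − Φ(z)]
- Of these, already above at baseline: 40 × [1 − 2Φ(z) + Φ₂(z, z; r)]
- New onset: the difference

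For example, with m = 420, s = 20, r = 0.8: z = 1.5 and 40 × 0.0668 = 2.67 are counted. Of these, 1.39 were already above, which is 1.39/2.67 = 52%. New onset is 2.67 − 1.39 = 1.28.

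| m | s | r | Counted per 40 | Already above at baseline | New onset |
|---|---|---|---|---|---|
| 410 | 20 | 0.6 | 0.91 | 0.22 (24%) | 0.69 |
| 410 | 20 | 0.8 | 0.91 | 0.39 (43%) | 0.52 |
| 410 | 25 | 0.6 | 2.19 | 0.70 (32%) | 1.49 |
| 410 | 25 | 0.8 | 2.19 | 1.10 (50%) | 1.09 |
| 420 | 20 | 0.6 | 2.67 | 0.91 (34%) | 1.76 |
| 420 | 20 | 0.8 | 2.67 | 1.39 (52%) | 1.28 |
| 420 | 25 | 0.6 | 4.60 | 1.88 (41%) | 2.72 |
| 420 | 25 | 0.8 | 4.60 | 2.66 (58%) | 1.94 |
| 430 | 20 | 0.6 | 6.35 | 2.90 (46%) | 3.45 |
| 430 | 20 | 0.8 | 6.35 | 3.91 (62%) | 2.44 |
| 430 | 25 | 0.6 | 8.47 | 4.29 (51%) | 4.18 |
| 430 | 25 | 0.8 | 8.47 | 5.53 (65%) | 2.94 |

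The written rule counts 0.9 to 8.5 of 40, and a new-onset rule counts 0.5 to 4.2. The share already above at baseline runs from 24% to 65%. New onset is not zero without a drug effect, so it still has to be read against placebo.

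**5. Large rises that stay at or below 450 msec**

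Assume a mean rise of 30 msec with s = 20 and r = 0.8. Half of the subjects, 20 of 40, rise by more than 30 msec. Of these, 60%, 40% or 22% end at or below 450 msec when m is 410, 420 or 430. That is 12, 8 or 4.4 of 40 in none of the visible QTcF categories.

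**The case against.** The strongest reply is that the section as a whole already covers this. Baseline counts are printed beside post-baseline counts, so an imbalance between arms at entry can be seen. Every individual change is listed, and the change summary gives the mean and the maximum by arm and visit. In step 5 the SD of the change is 20 × √(2 × 0.2) = 12.6 msec, so the mean rise of 30 msec would be shown with a standard error of 12.6/√40 = 2.0 msec per arm. A shift of that size would not be missed. The table is descriptive, and no primary endpoint or visible decision rule depends on it. All of this stands, and it keeps the point minor. It does not supply the number of subjects per arm who crossed a limit or had a large rise.

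A reader might infer more than the documents support:

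- **That large rises below 450 msec go uncounted.** The visible list ends at the foot of a page and the next page is not visible, so a second, change-based list may follow. Such a list would answer the part about large rises. The printed post-baseline counts would still mix old and new values.
- **That the post-baseline counts are mostly pre-existing values.** The range of 24-65% falls on both sides of one half, and the redacted criteria may limit entry.
- **That only one on-treatment ECG exists.** Protocol Table 1 and section 12.3 add Visit 14/ET. That visit is 14 ± 7 days after the last dose, but the synopsis counts those two weeks as part of the treatment period. SAP 7.6.5 also names Visit 8.
- **That chance differences between arms of 40 show this defect.** They come from small numbers, and new-onset counts have them too.

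**Conclusion.** The point holds as a minor weakness of a descriptive safety table. That the two counts cannot show crossings follows from the printed rule and needs no assumption. The size, about 24-65% of post-baseline values above 450 msec already present at baseline, rests wholly on assumed means, SDs and correlations and on no drug effect. It is an illustration, not an estimate for this trial. The absence of a count of large rises applies only to the visible text.

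A linked inconsistency needs settling because it decides which values enter the table. SAP 7.6.5 assumes pre- and post-infusion ECGs at Visits 4 and 8 and puts the pre-infusion value in the change summary. The protocol schedules one post-infusion ECG at Visit 4, shows none at Visit 8 in its visible text, and has one at Visit 14/ET. SAP 3.4.10 also allows for averaging triplicates, while protocol 11.1.5 describes single ECGs.

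**What to change.** In SAP 7.6.5:

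1. For each QT and QTcF limit, add a new-onset count. The numerator is subjects above the limit post-baseline and at or below it at baseline. The denominator is subjects at or below it at baseline with a post-baseline ECG. Alternatively, give a shift table from baseline to worst post-baseline value, and state whether unscheduled ECGs count towards the worst value. Keep the baseline row.
2. If the page that is not visible does not already do so, add counts of subjects with a QTcF increase from baseline >30 and >60 msec.
3. Reconcile the ECG visits, the pre- and post-infusion timing and the single or triplicate recording with the protocol, and state which value enters the outlier table at each visit.

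The cost is a few lines in the SAP and the table program. A baseline for each subject is already defined, so no new data are needed.
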